### **5.3.3. Sensitivity Analysis**

Sensitivity analyses of the primary efficacy variable will be based on the non-responder imputation (NRI) method. If a participant does not have the valid investigator-rated FWS assessment at maximum frown at any postintervention assessment through Day 7, he/she will be considered as a non-responder. CMH tests stratified by baseline investigator assessment of GL severity at maximum frown will be used for the analysis based on the imputed data. In addition, the pooled placebo group will be compared to each AGN study intervention group for proportion differences for the primary analysis.

### 5.3.4. Supplemental Approach

Categorical descriptive statistics including the sample size (N), frequency count, and percentage for each response score and change from baseline will be provided by study intervention group and by visit. Change from baseline values will be computed as the value for the postbaseline visit minus the baseline value.

[figure not shown]
[figure not shown]
## 5.4. Secondary and Exploratory Effectiveness Endpoint Analyses

### 5.4.1. Secondary and Exploratory Effectiveness Endpoints

Secondary effectiveness endpoints include:

- Achievement of a  $\geq$  2-grade improvement from baseline on the FWS according to **participant assessments** of GL severity at **maximum frown** at any postintervention timepoint through Day 7
- Achievement of a composite  $\geq$  2-grade improvement from baseline on the FWS at maximum frown as rated **concurrently by the investigator and participant** by timepoint
- Achievement of a  $\geq$  2-grade improvement from baseline on the FWS at maximum frown as rated by the **investigator** by timepoint
- Achievement of a  $\geq$  1-grade improvement from baseline on the FWS at maximum frown as rated by the **investigator** by timepoint
- Achievement of a  $\geq$  2-grade improvement from baseline on the FWS at maximum frown as rated by the **participant** by timepoint
- Achievement of a  $\geq$  1-grade improvement from baseline on the FWS at maximum frown as rated by the **participant** by timepoint
- None or mild rating in FWS at maximum frown as rated by **investigator** by timepoint
- None or mild rating in FWS at maximum frown as rated by **participant** by timepoint
- Responders (defined by primary endpoint) achieving none or mild FWS at maximum frown as rated by the **investigator** by timepoint

Exploratory effectiveness endpoints include:

CONFIDENTIAL  
AGN-151586

Statistical Analysis Plan Amendment 1

2034-201-008

CONFIDENTIAL  
AGN-151586

Statistical Analysis Plan Amendment 1

2034-201-008

#### **5.4.2. Main Analytical Approach**

The responder analyses will be analyzed in a similar way as for the primary effectiveness endpoint. The nominal p-values based on secondary effectiveness endpoints will be considered as supportive.

Descriptive statistics including the sample size (N), mean, standard deviation, median, 1st and 3rd quartiles, minimum, and maximum will be summarized by study intervention group and timepoint using the mITT Population for the FLO-11 item scores and total score, FLSQ item scores and domain scores.

#### **5.5. Safety Analyses**

Safety endpoints will be summarized by AGN-151586 dose group and placebo group in each cohort, as well as by total cohort groups and pooled placebo group and pooled AGN group using the Safety Population.

Study period in which events are experienced will be presented for safety data listings:

- 1 = screening period (prior to study intervention administration)
- 2 = treatment period (at time of study intervention administration)
- 3 = safety follow-up period (post-intervention through the end of study)

##### **5.5.1. Treatment Administration**

The treatment administration-related variables including the total dose will summarized by study intervention group using descriptive statistics.

Descriptive statistics will include the sample size (N), frequency count, and percentage for categorical endpoints, and sample size (N), mean, standard deviation, median, 1st and 3rd quartiles, minimum, and maximum for continuous endpoints.

##### **5.5.2. Adverse Events**

An adverse event (AE) will be considered a treatment-emergent adverse event (TEAE) if:

- The AE began on or after the date and time of the study intervention; or
- The AE was present before the date and time of the study intervention, but increased in severity or became serious on or after the date and time of the study intervention.

A TEAE will be considered a treatment-emergent serious adverse event (TESAE) if it is a TEAE that is also a serious adverse event (SAE).

A TEAE will be considered a treatment-related TEAE if it is considered related to the study intervention or study procedures by the principal investigator.

The number and percentage of participants with TEAEs as well as the events in the following AE categories will be summarized by study intervention group, as well as for all participants who received AGN-151586, as described in [Table 5-1](#).

If more than 1 AE is coded to the same preferred term for the same participant, the participant will be counted only once for that preferred term using the most severe and most related occurrence for the summarizations by severity and by relationship to study intervention.

Listings of all TEAEs, TESAEs, TEAEs leading to study discontinuation by participant, and death will be presented.

[figure not shown]
**Table 5-1 TEAE Tabular Summaries**

Endpoint	Description	Methodology
Overall summary	
Overall summary for the following categories:
 

• TEAEs

• Treatment-related TEAEs (including study drug-related TEAEs, study procedure-related TEAEs)

• TESAEs

• Treatment-related TESAEs

• Possible distant spread of toxin (PDSOT) TEAEs

• TEAEs leading to discontinuation from study

• Deaths

	Categorical descriptive summary statistics
TEAEs	

• Overall summary and by system organ class (SOC) and preferred term (PT)

• Overall summary and by SOC, PT, and maximum severity

• Overall summary and by PT in descending order

	Categorical descriptive summary statistics
Treatment-related TEAEs • Study drug-related TEAEs • Study procedure-related TEAEs	

• Overall summary and by SOC and PT

• Overall summary and by SOC, PT, and maximum severity

• Overall summary by maximum severity, duration, time to onset, resolution, and treatment required

	Categorical descriptive summary statistics, event descriptives
TESAEs	Overall summary and by SOC and PT if 5 or more participants overall reported such events	Categorical descriptive summary statistics
TEAEs leading to study discontinuation	Overall summary and by SOC and PT if 5 or more participants overall reported such events	Categorical descriptive summary statistics

In addition, neurologic assessments (Focused Symptoms Questionnaire and Focused Neurologic Examination) will be reported using descriptive statistics for baseline, follow-up visits, and for

the entire study period. Listings will also be provided. Treatment-emergent neurologic assessment-related AEs will be identified based on the abnormal findings and reported by SOC and PT.

To assess possible distant spread of toxin (PDSOT), MedDRA preferred terms that may be associated with botulinum toxin effects have been identified. The number and percentage of participants reporting TEAEs that are included in the PDSOT term list will be tabulated. Summary tables will be provided for participants with TESAEs and participants with TEAEs leading to discontinuation if 5 or more participants reported such events. In addition, all PDSOT AEs will be listed by subject. The terms are listed below.

### **5.5.3. Clinical Laboratory Assessments**

Descriptive statistics for clinical laboratory values (in International System of Units [SI] units) and changes from the baseline values at each assessment visit will be presented by study intervention group for the following laboratory parameters:

Hematology: Absolute and differential white blood cell count (neutrophil count, lymphocyte count, monocyte count, basophil count, eosinophil count), hemoglobin, hematocrit, platelet count, red blood cell count, and red blood cell indices (mean corpuscular volume, mean

corpuscular hemoglobin, and mean corpuscular hemoglobin concentration, and distribution width).

**Chemistry:** Sodium, potassium, calcium, chloride, bicarbonate, magnesium, inorganic phosphate, glucose, blood urea nitrogen, creatinine, total protein, alkaline phosphatase (ALP), albumin, total bilirubin (TBL), alanine aminotransferase (ALT), aspartate aminotransferase (AST), total cholesterol,  $\gamma$ glutamyl- transferase (GGT), lactate dehydrogenase (LDH), Uric acid

**Urinalysis:** Appearance, color, pH, specific gravity, glucose, protein, ketone, blood, urine microscopy

Clinical laboratory test values will be considered potentially clinically significant (PCS) if they meet either the lower-limit or higher-limit PCS criteria listed in [Table 6-3](#). The number and percentage of participants who have PCS postbaseline clinical laboratory values will be tabulated by study intervention group. The percentages will be calculated relative to the number of participants with available non-PCS baseline values and at least 1 postbaseline assessment. The numerator will be the total number of participants with available non-PCS baseline values and at least 1 PCS postbaseline value. A supportive tabular display of participants with PCS postbaseline values will be provided, including the PID number, baseline and all postbaseline (including non-PCS) values. In this listing, any participant with PCS value (if any) will also be included.

In addition, a tabular display showing all AEs that occurred in participants who had PCS postbaseline clinical laboratory values will be provided.

#### **5.5.4. Vital Signs**

Descriptive statistics for vital signs (ie, temperature, respiratory rate, pulse rate, systolic and diastolic blood pressure) and changes from baseline values at each assessment visit will be presented by study intervention group.

Vital sign values will be considered as PCS if they meet both the observed-value criteria and the change-from-baseline criteria listed in [Table 6-4](#). The number and percentage of participants with PCS postbaseline values will be tabulated by study intervention group. The percentages will be calculated relative to the number of participants with available non-PCS baseline values and at least 1 postbaseline assessment. The numerator will be the total number of participants with available non-PCS baseline values and at least 1 PCS postbaseline value. A supportive tabular display of participants with PCS postbaseline values will be provided, including the PID number, baseline and all postbaseline (including non-PCS) values.

In addition, a listing showing all AEs that occurred in participants who had PCS postbaseline vital sign values will be provided.

#### **5.5.5.      *Electrocardiogram***

Electrocardiogram (ECG) evaluations by investigators are captured in the eCRF and are classified into 3 categories: normal, abnormal, or not evaluable. These data will be summarized by study intervention group as change from baseline for each parameter, as well as the number and percent of participants in each category for PCS. Data listings which include ECG basic parameters and any ECG abnormalities will be produced.

#### **5.5.6.      *Pregnancy Test Analyses***

Urine pregnancy tests will be performed at the study center at screening, randomization/study intervention, and End of Study (Day 42 or Early Exit). Participants with a positive result will be presented in a listing for the Safety Population.

### **5.6.      *Other Analyses***

#### **5.6.1.      *Immunogenicity Analyses***

Immunogenicity results, manifested as the presence of binding antibodies (positive), and neutralizing antibodies (positive) after a validated assay becomes available, to AGN-151586, will be summarized in a table for baseline and postbaseline, if available by immunogenicity database lock. Immunogenicity findings (positive) will be tabulated with the number and percentage of participants at each visit separately for each AGN-151586 treatment group. Percentages will be based on the number of treated participants with interpretable antibody assays in each treatment group at the specified visit.

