Efficacy: To compare the efficacy between placebo and a range of doses of AGN-151586 for the treatment of GL in participants with moderate to severe GL	 Achievement of a ≥ 2-grade improvement from baseline on the FWS according to investigator assessments of GL severity at maximum frown at any postintervention timepoint through Day 7. 				
Safety: To compare the safety between placebo and a range of doses of AGN-151586 for the treatment of GL in participants with moderate to severe GL	Incidence of adverse events; change from baseline in hematology/chemistry/urinalysis laboratory, vital sign, and ECG parameters; and presence of antidrug antibodies				

Nonprimary assessments are specified in the SAP and COA SAP.

4. Study Design

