5.2. Exclusion Criteria

Participants are excluded from the study if any of the following criteria apply:

_	
1.	Medical Conditions
1.01	Any condition that precludes a participant's ability to comply with study requirements, including completion of the study visits or inability to read, understand, and/or self-assess GL severity using the FWS
1.02	Known immunization or hypersensitivity to any botulinum neurotoxin serotype
1.03	Known allergy or sensitivity to any of the components of the study interventions or any materials used in the study procedures
1.04	Any medical condition that may put the participant at increased risk with exposure to AGN-151586, including diagnosed myasthenia gravis, Eaton-Lambert syndrome, amyotrophic lateral sclerosis, or any other condition that might interfere with neuromuscular function
1.05	Any history of significant cardiovascular disease, family history of long QT syndrome, or a clinically significant ECG abnormality at the Screening Visit
1.06	Marked facial asymmetry, dermatochalasis, deep dermal scarring, excessively thick sebaceous skin, or the inability to substantially lessen facial lines even by physically spreading them apart, as determined by the investigator
1.07	Any brow or eyelid ptosis, as determined by the investigator
1.08	Infection or skin disorder at the injection sites
1.09	History of facial nerve palsy
1.10	Any uncontrolled systemic disease
1.11	Any medical condition that, in the opinion of the investigator, puts the participant at undue safety risk
1.12	History of alcohol or drug abuse within 3 months of randomization based on the investigator's judgment
1.13	Anticipated need for treatment with botulinum neurotoxin of any serotype for any reason during the study (other than study intervention)
1.14	Anticipated need for surgery or overnight hospitalization during the study

AGN-151586

2.	Prior/Concomitant Therapy
2.01	Reported use of any botulinum neurotoxin of any serotype for aesthetic treatment within the last 6 months prior to screening and for therapeutic treatment within the last 12 months prior to screening.
2.02	Any of the following procedures or treatments occurring in the specified period before randomization (Day 1):
	3 months : any facial nonablative resurfacing laser, light or ultrasound treatment, microdermabrasion, monopolar radiofrequency, or superficial peels

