8.8. Biomarkers and Other Assessments

Immunogenicity Assessments

Validated assays will be used to assess the presence of antidrug antibodies to AGN-151586, using blood samples collected during the course of the study.

Blood samples for immunogenicity testing will be collected from each participant at Screening, and at the Day 7, Day 28, and End-of-Study visits. Collected samples (approximately 20 mL per sample) will be processed to yield serum for analysis.

Detection of binding antibodies against AGN-151586 in participants' serum will be carried out using the validated ELISA in a 3-tier format (screening, confirmation, and titering). Only samples that are confirmed positive in the confirmatory assay will be stored and analyzed for presence of neutralizing antibodies to AGN-151586 when a validated assay becomes available.

These samples may also be used for additional characterization of antibody response to other neurotoxin subtype(s). The findings from this exploratory analysis will be documented in the clinical study report or in a separate report. The ICF will contain a separate appendix that addresses the use of immunogenicity samples for this optional exploratory research. The investigator or his/her representative will explain to each participant that their participation is voluntary. With regards to using their blood samples for this exploratory characterization of antibody response to other neurotoxin subtype(s), participants may give consent, refuse to give consent, or may give consent and later withdraw their consent at any time and for any reason

AGN-151586

during the storage period. A separate signature will be required to document a participant's agreement or refusal to allow specimens to be used for this exploratory research.

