## 1.1. Objectives and Endpoints

Objectives	Endpoints
Primary	

• Efficacy: To compare the efficacy between placebo and a range of doses of AGN-151586 for the treatment of GL in participants with moderate to severe GL

• Safety: To compare the safety between placebo and a range of doses of AGN-151586 for the treatment of GL in participants with moderate to severe GL

Secondary	

• To compare the efficacy between placebo and a range of doses of AGN-151586 for the treatment of GL in participants with moderate to severe GL, as measured by the FWS (participant-assessed, investigator-assessed)

• Achievement of a <math>\ge 2</math>-grade improvement from baseline on the FWS according to investigator assessments of GL severity at maximum frown at any postintervention timepoint through Day 7

• Incidence of AEs; change from baseline in hematology/chemistry/urinalysis laboratory, vital sign, and ECG parameters; and presence of antidrug antibodies

• Achievement of a <math>\ge 2</math>-grade improvement from baseline on the FWS according to participant assessments of GL severity at maximum frown at any postintervention timepoint through Day 7

• Achievement of a composite <math>\ge 2</math>-grade improvement from baseline on the FWS at maximum frown as rated concurrently by the investigator and participant by timepoint

• Achievement of a <math>\ge 2</math>-grade improvement from baseline on the FWS at maximum frown as rated by the investigator by timepoint

• Achievement of a <math>\ge 1</math>-grade improvement from baseline on the FWS at maximum frown as rated by the investigator by timepoint

• Achievement of a <math>\ge 2</math>-grade improvement from baseline on the FWS at maximum frown as rated by the participant by timepoint

• Achievement of a <math>\ge 1</math>-grade improvement from baseline on the FWS at maximum frown as rated by the participant by timepoint

• None or mild rating in FWS at maximum frown as rated by investigator by timepoint

• None or mild rating in FWS at maximum frown as rated by participant by timepoint

• Responders (defined by primary endpoint) achieving none or mild FWS at maximum frown as rated by the investigator by timepoint

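### SAP 5.6.1 plans the by-visit antibody table for AGN-151586 groups only, against the placebo-comparison objective and SAP 5.1 and 5.5, and defines no treatment-emergent rate

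*SAP*

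**What the plan says.** The primary safety objective in Protocol Section 3 is "To compare the safety between placebo and a range of doses of AGN-151586", and its endpoint ends with "vital sign, and ECG parameters; and presence of antidrug antibodies". SAP 1.1 carries the same endpoint: "change from baseline in hematology/chemistry/urinalysis laboratory, vital sign, and ECG parameters; and presence of antidrug antibodies".

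Sampling covers both arms. Protocol 8.8 states: "Blood samples for immunogenicity testing will be collected from each participant at Screening, and at the Day 7, Day 28, and End-of-Study visits". The assay is a validated ELISA with screening, confirmation and titering tiers.

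SAP 5.6.1, under Other Analyses, first promises a table for baseline and postbaseline, without naming arms. It then specifies: "Immunogenicity findings (positive) will be tabulated with the number and percentage of participants at each visit separately for each AGN-151586 treatment group". On the denominator it adds: "Percentages will be based on the number of treated participants with interpretable antibody assays in each treatment group at the specified visit".

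Two general rules in the same SAP are wider. Section 5.1 has effectiveness and safety endpoints summarized by intervention group within each cohort, and it names both AGN-151586 and placebo. Section 5.5 does the same for safety endpoints and adds pooled placebo and pooled AGN-151586 groups. SAP 6.2 declares one departure from the protocol's analyses (TEAEs in place of AEs), and it does not concern antibodies.

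**The concern.** There are two separate gaps.

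- **Comparator.** The only text that specifies the by-visit antibody table names active groups alone. A programmer who follows the specific section over the general ones would produce no placebo column for a component of the primary safety endpoint. The placebo rate is what shows how often this assay reads positive, at the same visits, in people not given the toxin.
- **Treatment-emergent response.** The percentage at each visit is not limited to participants who were negative at Screening, and no rule defines an induced or boosted response. The post-baseline rows then mix participants who were already positive with those who became positive, so the table does not give the rate of new antibody formation in each dose group.

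**Working it through.** The documents state no antibody rate and no sample-size reasoning for immunogenicity, so there is no figure of the plan's own to reproduce. The check is a reading of the rules side by side, followed by arithmetic for scale.

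**1. Which arms are covered**

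| Place | Arms |
|---|---|
| Protocol Section 3, SAP 1.1 (objective and endpoint) | Doses compared with placebo |
| Protocol 8.8 (sampling) | Every participant |
| SAP 5.1 (general rule) | AGN-151586 and placebo, per cohort |
| SAP 5.5 (safety endpoints) | AGN-151586 and placebo, per cohort and pooled |
| SAP 5.6.1 (by-visit antibody table) | AGN-151586 groups only |

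Section 5.6.1 is the one row that leaves placebo out. It lies outside 5.5, and 6.2 does not declare a change.

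**2. How participants positive before treatment are handled**

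The only pre-treatment antibody sample is at Screening, so under the baseline definition in SAP 5.1 that sample is the baseline. In 5.6.1 the numerator is positives at the visit and the denominator is all treated participants with an interpretable assay at that visit. It follows that someone positive at Screening and still positive later is in the numerator each time. By contrast, the percentages for potentially clinically significant (PCS) laboratory and vital-sign values in SAP 5.5.3 and 5.5.4 are restricted to participants with non-PCS baseline values.

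**3. Scale**

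Inputs: 30 on AGN-151586 and 10 on placebo per cohort, up to five cohorts (Protocol 9.2), hence about 150 and 50. All samples are taken as interpretable.

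- One persistent Screening positive: 1/30 = 3.3 points on each later row of that dose group, and the same on its baseline row.
- Assume 2 of 30 positive at Screening and persistent, none new. By-visit rate: 2/30 = 6.7%. Treatment-emergent rate: 0/28 = 0%.
- Assume 2 of 30 positive at Screening and persistent, 1 new. By-visit rate: 3/30 = 10.0%. Treatment-emergent rate: 1/28 = 3.6%.
- Assume 2 positives revert and 2 others convert. The baseline and later rows both read 2/30, so the table shows no change.

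The chance that a group of n has at least one Screening positive is 1 − (1 − q)^n, with q assumed:

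| q (assumed) | n = 30 (one dose) | n = 50 (pooled placebo) |
|---|---|---|
| 1% | 26% | 39% |
| 2% | 45% | 64% |
| 5% | 79% | 92% |

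**4. What placebo columns can show**

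If no placebo participant is positive, the upper limit of the exact two-sided 95% interval is 1 − 0.025^(1/n). This gives 30.8% for n = 10 and 7.1% for n = 50. A single cohort's placebo group says little about background; the pooled group says considerably more. Both columns are worth having, but the pooled one carries most of the information.

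**The case against.** The strongest reply is that placebo is already covered. Antidrug antibodies are a safety endpoint, so SAP 5.1 applies and 5.5 arguably does too. The opening sentence of 5.6.1 and Protocol 9.4.3.1 restrict no arm, and the denominator sentence in 5.6.1 refers simply to each treatment group. This stands in part. A reader might infer from 5.6.1 that the placebo samples will go unused or that the comparison cannot be made; the general rules do not support that. What remains is that the most specific sentence contradicts the general ones.

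Second, 5.6.1 requires a baseline summary, so the group's background is visible. That is correct, and a reader should not infer that the SAP hides earlier positivity or states that pre-existing antibodies are an effect of treatment. It says neither. Counting them at later visits follows from the per-visit rule, and what the table lacks is conversion within participants.

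Third, a reader might infer that earlier toxin users will bring many reactive antibodies. Criterion 2.01 excludes only recent use ("Reported use of any botulinum neurotoxin of any serotype for aesthetic treatment within the last 6 months prior to screening", with 12 months for therapeutic use), so earlier users can enter. But criterion 1.02 excludes known immunization to any serotype, the protocol describes current treatment as serotype A, and the assay targets a serotype E product and includes a confirmation step. Nothing in the documents shows that earlier exposure reads positive in this assay. Baseline positives are possible; their frequency is unknown.

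Finally, table specifications are in a separate document, which may already contain placebo columns or a conversion table. That cannot be checked here, but it would not remove the contradiction in the SAP text.

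**Conclusion.** The point holds as an internal conflict and a missing definition. SAP 5.6.1 names only AGN-151586 groups for the by-visit table of a primary safety component, against the objective and against SAP 5.1 and 5.5. Its percentage is a prevalence, and no treatment-emergent rate is defined, although the SAP uses a baseline-restricted denominator for PCS laboratory and vital-sign values.

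The size is modest and conditional: 3.3 points per persistent Screening positive in a dose group of 30, if all 30 samples are interpretable. The background rates of 1%, 2% and 5% in the working are assumptions used only for scale. Immunogenicity is summarized descriptively with no test attached, so the efficacy analysis is unaffected and no data are lost. It is still worth correcting, because the placebo comparison stated as a primary objective should not depend on which section of the SAP a programmer follows.

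**What to change.** Amend SAP 5.6.1 as follows:

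1. Reconcile it with 5.1 and 5.5 by adding placebo columns, by cohort and pooled, beside the AGN-151586 groups.
2. Keep the by-visit table and label it as prevalence.
3. Add treatment-emergent positivity: negative at Screening and confirmed positive at any later visit, as a percentage of Screening-negative participants with at least one interpretable post-baseline sample.
4. List titres over time for participants positive at Screening, in both arms.

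The Screening samples, placebo samples and titering step are already in Protocol 8.8. The cost is SAP wording and table shells; no visit, sample or participant is added.
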